## 2. Hypothesis of the Biomedical Research

Community-implemented social and physical environmental interventions promoting higher physical activity will have a positive effect on the health of children and adolescents living in disadvantaged social and economic conditions and will contribute to improving health equity in this group.

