## 3. Objective of the Biomedical Research

The Connection project aims to develop, implement, and evaluate co-created community-based social and physical environmental interventions that promote healthier eating and increased physical activity among children and adolescents living in disadvantaged social and economic conditions, with the main goal of improving health equity.

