## 4. Tasks of the Biomedical Research

The tasks of the Connection study are:

1. Collect data on residential air pollution (PM2.5, PM10, and NO2) and determine its associations with children's physical health.
2. Gather information on children's physical activity, dietary habits, sleep quality, and health behaviour.
3. Assess parents' and children's attitudes toward health and the living environment.
4. Evaluate the impact of physical activity and sleep on children's health.
5. Assess the effectiveness of smart wristbands as a tool for monitoring physical activity, sleep, and heart function.
6. Reassess children's health indicators after 3 months and compare them with baseline data.

**5. Detailed Description of the Study Outcomes** (Primary and Secondary Study Endpoints)  
The Connection project will evaluate the following outcomes

Primary outcomes: Children's blood pressure, anthropometric data (height, weight), body fat percentage, physical activity levels, depending on exposure, socioeconomic status, and healthy lifestyle.

Secondary outcomes: Children's well-being depending on exposure, socioeconomic status, and healthy lifestyle.

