## 6. Justification of the Biomedical Research

This new international study is conducted at Vytautas Magnus University under the European Commission's ERA4health call, funded by the Research Council of Lithuania. The international project coordinator is the University of Porto, Portugal. Poor nutrition and insufficient physical activity are among the main behavioural risk factors for non-communicable diseases.. A higher prevalence of unhealthy behaviours in lower socio-economic groups is one of the mechanisms linking disadvantaged social and economic conditions to poorer health indicators. Furthermore, diet and physical activity are potentially modifiable behavioural factors that partly explain socio-economic differences in morbidity and mortality. Promoting positive behaviours, particularly among people of lower social status, is a public health priority. Therefore, changes in social norms and living environments that shape behaviour, encouraging individuals to adopt more balanced dietary habits and be physically active, should be considered essential primary prevention measures to promote health and well-being. Target populations and various stakeholders should actively participate in designing, implementing, and evaluating measures aimed at creating healthier and more sustainable environments.

Based on the WHO's "health in all policies" concept, these interventions should integrate public health approaches to tackle complex problems and emphasize the importance of scientific progress, public awareness and advocacy, consumer demand, industrial innovations, government regulation, and cultural changes.

The effectiveness of public health strategies may vary among social and economic groups and may even increase inequality. Adverse environmental influences and negative social incentives are particularly strong and have a profound impact on children and adolescents growing up in disadvantaged neighbourhoods, exposing them to higher health risks. Young people living in unfavourable conditions are particularly difficult to engage in current programs and therefore do not benefit from existing community interventions. Changing nutrition, physical activity, and movement habits is a complex and time-consuming process that requires involving community members and local authorities and empowering them. The engagement process should be particularly attentive to people living in vulnerable conditions.

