## 8. Methodology of the Biomedical Research

The Connection study consists of two stages: a cross-sectional study (initial research) and an in-depth interventional study. These stages are interconnected and aim to assess children's health and physical parameters as well as the impact of environmental factors:

1. **Cross-sectional study (initial research):** This stage will include children aged 12–16 attending VDU Atžalynas Progymnasium. Approximately 200 children ( $\pm 10\%$ ) will be randomly selected to participate once.

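### Improved health equity is the hypothesis and main goal, but no outcome is a change in a socioeconomic gap, and about 20 re-measured children cannot support a conclusion on it

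*Protocol*

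**What the plan says.** The hypothesis in Section 2 of the protocol concerns children in disadvantaged conditions. It predicts a health benefit and adds that the interventions "will contribute to improving health equity in this group". Section 3 describes the project's interventions "with the main goal of improving health equity". Section 6 gives a reason for caution: "The effectiveness of public health strategies may vary among social and economic groups and may even increase inequality".

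The primary outcomes in Section 5 are blood pressure, height and weight, "body fat percentage, physical activity levels, depending on exposure, socioeconomic status, and healthy lifestyle". The secondary outcome is "well-being depending on exposure, socioeconomic status, and healthy lifestyle". The only longitudinal task in Section 4 is task 6: "Reassess children's health indicators after 3 months and compare them with baseline data".

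Under Section 8, about 200 children from one school "will be randomly selected to participate once" in the cross-sectional stage. About 10% of them, around 20, enter the in-depth stage, and these are re-measured at 3 months. Section 13 draws them from children who said they were willing. It mentions no stratification by SES. SES information comes from the parent questionnaire.

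**The concern.** To say that equity has improved, one must show that a difference between better-off and worse-off children has become smaller. That needs the difference at two times or, equivalently, the change compared between SES groups. The protocol names neither as an outcome. It names individual measurements that may depend on SES, and a before-after comparison over all re-measured children.

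The protocol's own warning shows what is at stake. If an intervention can widen inequality, an average improvement says nothing about its direction. The study could report better blood pressure or activity at 3 months and be read as having met its main goal, although the gap had stayed the same or grown. A statistical analysis plan can choose a model, but it cannot alter the hypothesis or enlarge the re-measured sample that the protocol sets.

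**Working it through.** **Step 1. Set the claim beside the outcomes.**

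| Place in the protocol | What it provides | A change in an SES difference? |
|---|---|---|
| Sections 2 and 3 | Improved equity as hypothesis and main goal | This is what is claimed |
| Section 5, primary and secondary outcomes | Individual measurements depending on SES and other factors | Not named |
| Section 4, task 6 | 3-month values against baseline | Not named |
| Section 8, cross-sectional stage | About 200 children, measured once | Not possible, one time point |
| Sections 8 and 13, in-depth stage | About 20 willing children, measured twice | Possible in principle, but see step 3 |

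**Step 2. Reproduce the plan's own figure.** The size of the in-depth stage is a sampling fraction: 0.10 × 200 = 20. With 200 ± 10%, that is 180 to 220 children, and 10% of these is 18 to 22, which matches the ± 2 in Section 7. The available text gives no power, effect size or significance level.

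**Step 3. What 20 children could show about a change in the gap.** Read the outcomes generously and suppose that 3-month change is compared between two SES groups.

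Assumptions, none of them from the protocol: binary SES split, two-sided 5%, 80% power, no dropout. The unit is the SD of the 3-month change.

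- Standard error: SE = √(1/n₁ + 1/n₂). For 10/10: √0.2 = 0.447. For 5/15: √(0.2 + 0.0667) = 0.516.
- 95% half-width: t(0.975; 18 df) × SE, with t = 2.101. For 10/10: 2.101 × 0.447 = 0.94. For 5/15: 2.101 × 0.516 = 1.08.
- Detectable difference, normal approximation: (1.96 + 0.84) × SE. For 10/10: 1.25. For 5/15: 1.45.
- Detectable difference, noncentral t with 18 df: 1.33 for 10/10 and 1.53 for 5/15.

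Sensitivity (noncentral t): 9/9 gives 1.41, 11/11 gives 1.26, 12/8 gives 1.35 and 16/4 gives 1.66. If dropout left 8/8, it would be 1.51. For a given total, the equal split is the most favourable. With 10/10, power is about 18% for a difference in change of 0.5 SD. Detecting that would take 2 × 2.80² / 0.5² ≈ 63 children per SES group.

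**Step 4. Convert to baseline SDs.** With equal variances at both times and a correlation r between baseline and 3 months, SD of change = baseline SD × √(2(1 − r)). The 10/10 figure of 1.33 then becomes about 1.3 baseline SDs at r = 0.5, 0.84 at r = 0.8 and 0.59 at r = 0.9. The values of r are assumed. The limit is therefore less severe for stable measures such as height and weight.

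**Step 5. What the cross-sectional stage can show.** For a one-time SES difference in 200 children, the 95% half-width is 1.972 × √(1/100 + 1/100) = 0.28 SD for 100/100 and 1.972 × √(1/50 + 1/150) = 0.32 SD for 50/150. These are SDs of the measurement itself, so they must not be set directly against the figures in step 3. They describe a level at one time, not a change.

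**The case against.** Four points can be made for the plan.

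- **Equity may be a programme aim.** Section 3 speaks of the project, Section 6 describes an international study, and Section 18 provides for sharing coded data with consortium partners. Equity might be assessed on pooled data under an international protocol that is not at hand. This stands as a reason not to demand that the goal be deleted. It does not answer the point for this protocol, which places the prediction under its own hypothesis.
- **Change by SES is compatible with the outcomes.** The phrase "physical activity levels, depending on exposure, socioeconomic status, and healthy lifestyle" is not limited to baseline, and how SES enters a model may be left to the analysis plan. That is true, but the only children with a change to analyse are the 20 or so in step 3, and the analysis plan cannot add to them.
- **No equity conclusion is promised.** The tasks contain none, and Section 23 speaks of recommendations on physical activity. This lowers the risk, but a stated hypothesis invites a conclusion.
- **The numbers rest on assumptions.** SES could be continuous or ordered, and significance level, power and split are not given. This stands. The mismatch between claim and outcomes does not depend on them.

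Two stronger readings are tempting. A reader might infer that equity logically cannot improve within one group, so that the hypothesis contradicts itself. The wording is loose: it can mean disadvantaged children catching up with others, or a gradient among disadvantaged children. A reader might also infer that the baseline SES gap in the 200 children could serve as the equity result. It can describe inequality, but a single time point carries no evidence of improvement.

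**Conclusion.** The point holds as a mismatch between the hypothesis and what this study measures. As written, the plan cannot confirm or refute the equity part of its hypothesis. No task or outcome is a change in an SES difference, and in the available text (Section 9 was not part of it) the only repeated measurements are in about 20 willing children, without stated SES stratification or a comparison group.

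If change were nevertheless compared by SES, the interval would be about ± 0.94 SD of the 3-month change at best (10/10), and 80% power would need about 1.3 SD; for 5/15 these are about 1.1 and 1.5. This assumes a binary SES split, a two-sided 5% level and no dropout, and it is smaller in baseline SDs for stable measures. Even a clear change in the gap could not be attributed to the intervention without a comparison group.

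The documents do not support the wider inference that the consortium's equity goal is untestable. The limit applies to what this study may conclude.

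**What to change.** - **Sections 2 and 3:** keep equity as the long-term or consortium-level aim, and state that this study does not test whether equity improves.
- **Section 5, cross-sectional stage:** report the one-time SES differences in the listed primary outcomes in the roughly 200 children with confidence intervals, labelled as a description of existing inequality and not of improvement.
- **Section 5, in-depth stage:** report 3-month change by SES in the roughly 20 children descriptively with intervals, and state that no conclusion on improved equity will be drawn from it.

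The cost is a more modest stated claim, plus the approvals that Section 19 requires for a protocol change. No new data are needed, because the parent questionnaire already collects social and demographic information.

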## 3. Objective of the Biomedical Research

The Connection project aims to develop, implement, and evaluate co-created community-based social and physical environmental interventions that promote healthier eating and increased physical activity among children and adolescents living in disadvantaged social and economic conditions, with the main goal of improving health equity.

## 4. Tasks of the Biomedical Research

The tasks of the Connection study are:

1. Collect data on residential air pollution (PM2.5, PM10, and NO2) and determine its associations with children's physical health.
2. Gather information on children's physical activity, dietary habits, sleep quality, and health behaviour.
3. Assess parents' and children's attitudes toward health and the living environment.
4. Evaluate the impact of physical activity and sleep on children's health.
5. Assess the effectiveness of smart wristbands as a tool for monitoring physical activity, sleep, and heart function.
6. Reassess children's health indicators after 3 months and compare them with baseline data.

**5. Detailed Description of the Study Outcomes** (Primary and Secondary Study Endpoints)  
The Connection project will evaluate the following outcomes

Primary outcomes: Children's blood pressure, anthropometric data (height, weight), body fat percentage, physical activity levels, depending on exposure, socioeconomic status, and healthy lifestyle.

Secondary outcomes: Children's well-being depending on exposure, socioeconomic status, and healthy lifestyle.

## 6. Justification of the Biomedical Research

This new international study is conducted at Vytautas Magnus University under the European Commission's ERA4health call, funded by the Research Council of Lithuania. The international project coordinator is the University of Porto, Portugal. Poor nutrition and insufficient physical activity are among the main behavioural risk factors for non-communicable diseases.. A higher prevalence of unhealthy behaviours in lower socio-economic groups is one of the mechanisms linking disadvantaged social and economic conditions to poorer health indicators. Furthermore, diet and physical activity are potentially modifiable behavioural factors that partly explain socio-economic differences in morbidity and mortality. Promoting positive behaviours, particularly among people of lower social status, is a public health priority. Therefore, changes in social norms and living environments that shape behaviour, encouraging individuals to adopt more balanced dietary habits and be physically active, should be considered essential primary prevention measures to promote health and well-being. Target populations and various stakeholders should actively participate in designing, implementing, and evaluating measures aimed at creating healthier and more sustainable environments.

Based on the WHO's "health in all policies" concept, these interventions should integrate public health approaches to tackle complex problems and emphasize the importance of scientific progress, public awareness and advocacy, consumer demand, industrial innovations, government regulation, and cultural changes.

The effectiveness of public health strategies may vary among social and economic groups and may even increase inequality. Adverse environmental influences and negative social incentives are particularly strong and have a profound impact on children and adolescents growing up in disadvantaged neighbourhoods, exposing them to higher health risks. Young people living in unfavourable conditions are particularly difficult to engage in current programs and therefore do not benefit from existing community interventions. Changing nutrition, physical activity, and movement habits is a complex and time-consuming process that requires involving community members and local authorities and empowering them. The engagement process should be particularly attentive to people living in vulnerable conditions.

Moreover, previous research shows that, in youth populations, there is increasing interest in addressing food surplus and food-sharing practices in school catering facilities and food education activities as a way to tackle social nutritional disparities.

## 7. Description of Study Participants

The Connection study will include children aged 12–16 attending VDU Atžalynas Progymnasium. Selection will be random, involving approximately 200 children ( $\pm 10\%$ ) who will participate in the initial cross-sectional study. From these participants, about 10% (around 20 children  $\pm 2$ ) will be invited to take part in an in-depth interventional study. All children participating in the study

will be required to sign informed consent forms together with their parents (or legal guardians) and will be allowed to choose in which phase of the study they wish to participate.

Children will be excluded from the study if they do not meet the age criteria (younger than 12 or older than 16 years), if their parents or guardians refuse to sign the informed consent form, if they have health conditions that could interfere with the study or pose a health risk, or if they are unwilling to comply with study requirements, such as refusing to wear a smart wristband.

## 8. Methodology of the Biomedical Research

The Connection study consists of two stages: a cross-sectional study (initial research) and an in-depth interventional study. These stages are interconnected and aim to assess children's health and physical parameters as well as the impact of environmental factors:

1. **Cross-sectional study (initial research):** This stage will include children aged 12–16 attending VDU Atžalynas Progymnasium. Approximately 200 children ( $\pm 10\%$ ) will be randomly selected to participate once.

### Study procedures:

Children and their parents will be asked to complete questionnaires:

- **Child questionnaire:** Covers health behaviour, well-being, and environmental assessment.
- **Parent questionnaire:** Covers social and demographic indicators, home address (required for individual air pollution assessment).

Measurements for children will include:

- Blood pressure;
- Anthropometric measurements: height (cm) and weight (kg);
- Body composition analysis.

All devices will have CE certification. Filling in the questionnaires will take up to 20 minutes, and measurements up to 10 minutes. The total procedure duration will be about 30 minutes. The collected questionnaire data will include social, demographic, health behaviour, well-being, and environmental assessment indicators. Information will be coded to prevent linking a child's name to the ID number. Data from paper questionnaires will be entered into computer software. All data will be recorded on digital data collection sheets and stored in the research database following data protection requirements.

2. **In-depth interventional study:** This stage will involve about 10% of the participants from the cross-sectional study (around 20 children) who agree to take part in a 7-day physical activity monitoring study.

### Study procedures:

Participants will attend a two-visit program:

First visit: Initial assessment during which:

- A CE-certified smart wristband is placed on the participant to monitor physical activity, heart function, and sleep quality for 7 days.
- After 7 days: Participants return the wristbands and provide verbal feedback about their study experience.

Second follow-up visit after 3 months:

 Prietaisaias Omron M3W (HEM-7202-E(V))

 Prietaisaias Kern MPE (250K100HM)

 Prietaisaias Tanita MC780

- Blood pressure, height, weight, and body composition are re-measured (duration up to 10 minutes).
- Participants wear smart wristbands again for 7 days.
- After 7 days: Participants return the wristbands and complete a short questionnaire about their experience.

Data on residential addresses collected during the cross-sectional study will be linked to the environmental pollution database (PM2.5, PM10, NO2) and children's physical health indicators. During the in-depth study, changes in physical activity and sleep will be analysed to assess the impact of the intervention on health. All participants will be informed about the study aims and procedures. Participation is voluntary, and all data will be coded and protected according to data protection regulations. No methods used in either stage are expected to cause adverse or long-term health effects.

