## **11. Duration of Participant Involvement in the Biomedical Research**

Participant involvement depends on the study stage:

Cross-sectional study: One-time participation lasting up to 30 minutes (20 minutes for questionnaires, 10 minutes for measurements).

In-depth study: Two 7-day periods of wearing a smart wristband, two visits, and a follow-up assessment after 3 months (total: ~20 minutes per visit).

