## **13. Procedure for Inviting Participants to the Biomedical Research**

The invitation of participants to the biomedical research will be organized in close cooperation with VDU Atžalynas Progymnasium, whose students constitute the target study group. The target group for this research is children aged 12–16.

The school administration and teachers will be introduced to the aim of the study, methodology, and participant selection criteria. With the school's assistance, an effective information dissemination channel will be ensured. Information invitations to participate in the study will be distributed to potential participants and their parents, clearly presenting the study's purpose, procedures, potential benefits and risks, and participation conditions. Parents will also be informed via school email or other internal communication systems. Invitations will be sent through electronic diaries or other school information channels.

Information meetings will be organized to allow parents and students to learn about the study's objectives, ask questions directly to the researchers, and receive detailed answers. These meetings aim to ensure that potential participants and their parents make an informed decision about participation. After these meetings, informed consent forms will be distributed to parents, who will be asked to complete and return them if they agree to participate. Children will also sign a consent form adapted to their level of understanding.

Participants for the cross-sectional study will be randomly selected from students who agreed to participate. Later, participants for the interventional part of the study will be selected based on the 10% sampling principle, from those who indicated willingness to take part in the in-depth study in the questionnaires.

This procedure ensures that participants and their parents receive comprehensive information, can make an informed choice about participation, and that the recruitment process is transparent and effective.

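### The in-depth stage is meant to assess an intervention's impact on health, but as described it is one group of about 20 children measured before and after with no concurrent comparator, so it cannot attribute a change to an intervention

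*Protocol*

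**What the plan says.** The hypothesis in Section 2 is causal: "Community-implemented social and physical environmental interventions promoting higher physical activity will have a positive effect on the health" of disadvantaged children and adolescents. Section 3 includes evaluating such interventions in the project's objective. Section 8 carries this aim into the second stage, where "changes in physical activity and sleep will be analysed to assess the impact of the intervention on health".

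The same protocol describes that stage as follows.

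- **Who takes part.** About 10% of the cross-sectional sample, around 20 ± 2 children, "will be invited to take part in an in-depth interventional study" (Section 7). They are chosen "from those who indicated willingness to take part in the in-depth study in the questionnaires" (Section 13).
- **What they agree to.** Section 8 refers to children "who agree to take part in a 7-day physical activity monitoring study".
- **What is done.** Section 11 gives a single schedule: "Two 7-day periods of wearing a smart wristband, two visits, and a follow-up assessment after 3 months". The Section 8 lists add verbal feedback after the first wristband week, a short questionnaire after the second, and at the 3-month visit: "Blood pressure, height, weight, and body composition are re-measured".
- **What the others do.** The roughly 200 cross-sectional children "will be randomly selected to participate once" (Section 8), and Section 11 confirms a single contact.
- **What is compared.** Task 6 in Section 4 compares the health indicators after 3 months with baseline.

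**The concern.** The sentence in Section 8 promises a causal conclusion, and the design described beside it cannot deliver one. To attribute a change to an intervention, one must know what would have happened to similar children over the same months without it. Nothing in the available text provides that: no allocation, no comparison school, and no second measurement of the children outside the in-depth group.

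The protocol also sits uneasily with itself. It calls the stage interventional, yet the listed procedures only measure, and Task 5 in Section 4 treats the wristband as a monitoring tool.

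The stakes are practical. Section 23 plans to use the results to develop recommendations on raising students' physical activity. A 3-month change of unknown cause, reported as impact, could feed into them.

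**Working it through.** **1. Size of the stage.** Section 7 gives about 200 children ± 10% and an in-depth share of about 10%. 0.10 × 200 = 20, 0.10 × 180 = 18 and 0.10 × 220 = 22. This reproduces the stated 20 ± 2.

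**2. Search for a comparator.** Three candidates can be checked.

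- A second arm within the in-depth stage: none is described. All these children follow the same schedule (Sections 8 and 11).
- The roughly 200 − 20 = 180 other cross-sectional children: they are measured once, so they have no change score.
- The child's own baseline: this is the planned comparison. It removes stable differences between children but not anything that changes between the two measurements.

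**3. What the mean change contains.** Write the expected mean change in the single group as

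E(change) = τ + s + c + (r₂ − r₁) + g

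Here τ is any intervention effect, s is season, c is the school calendar, r₁ and r₂ are the reactions to wearing the wristband in the first and second weeks, and g is growth at ages 12 to 16. A constant reaction cancels (r₂ = r₁), but a changing one does not. Growth bears mainly on the re-measured height, weight and body composition. The design yields one mean change per outcome, so τ cannot be separated from the sum of the other terms. A concurrent comparison group would give a second equation without τ. The difference would then isolate τ, provided the other terms are equal in both groups.

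The number of children does not appear in this expression, so a larger group leaves the problem as it is.

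**4. What the stage can estimate, and how precisely.** The 95% confidence interval half-width for a mean within-child change, in units of the SD of change, is t(0.975, n − 1)/√n:

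- n = 18: 2.110/4.243 = 0.497
- n = 20: 2.093/4.472 = 0.468
- n = 22: 2.080/4.690 = 0.443
- n = 200, for contrast only: 1.972/14.142 = 0.139

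**5. Illustration that size does not help.** Assume a two-sided 5% paired t-test, no intervention effect, and a mean shift from other causes. The shifts are assumptions; the protocol gives no such figures. With 20 children, a shift of 0.25 SD of change is significant in about 19% of studies and one of 0.50 SD in about 56%. With 200 children the rates are about 94% and over 99%. A bigger single group would report a spurious impact more often.

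**The case against.** **The intervention may be defined elsewhere.** The text between Sections 8 and 10 was not available to this review, and Section 18 mentions an international protocol that was not available either. This stands as a limit. A reader might infer that no intervention exists, or that none reaches these children. The documents do not support that; one can say only that the procedure lists in Section 8 contain none. The comparator point is firmer, because Sections 8 and 11 give a second measurement to the in-depth children alone. An intervention defined elsewhere would still leave a before-after comparison in one group.

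**An analysis plan could deal with growth.** This stands in part. Age- and sex-standardised scores could reduce the expected growth component in height and weight. They do nothing for season, school calendar or a changing reaction to the wristband.

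**The claim is one sentence, and none of the six tasks in Section 4 is to evaluate an intervention.** This is true, and it makes the correction easy. However, the sentence agrees with the causal hypothesis in Section 2 and the objective in Section 3, so it cannot be dismissed as a slip.

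**The size of the bias is unknown.** This also stands. A reader might infer a definite seasonal or growth bias of a stated size, but the documents give neither the magnitudes nor the start dates. If all children started together with the two weeks placed symmetrically about a seasonal peak or trough, the seasonal part could be zero. The growth interval is not fixed at 3 months either. Height and weight are first listed at the cross-sectional visit, the first in-depth visit lists only the wristband, and Section 13 says only that in-depth selection comes later.

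**Conclusion.** The concern holds for the impact claim. As described, the in-depth stage can show that activity, sleep or health indicators changed, but not that an intervention changed them. This follows from the single group and the one-time participation of the other children. It does not depend on the sample size, the choice of test, or any assumed amount of drift. The bias cannot be sized from the documents.

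It would be wrong to read this as a complaint that 20 children are too few. A half-width of about 0.47 SD of change (0.50 at 18, 0.44 at 22) is simply the precision of a descriptive estimate, and more children would sharpen that estimate without making it causal. Nor is the stage without value: within-child change, associations of activity and sleep with health indicators, and the usefulness of the wristband remain legitimate aims. Choosing from willing children limits how far the results generalise, but it is not the source of the attribution problem.

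The conclusion rests on the available text giving the full follow-up schedule. If unavailable text provides a concurrent group re-measured at 3 months, the protocol should refer to it here and the point would be met.

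**What to change.** Replace the sentence in Section 8 with:

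> The in-depth stage estimates within-child change from baseline to the 3-month follow-up in physical activity, sleep, blood pressure, height, weight and body composition, with 95% confidence intervals, describes the associations of physical activity and sleep with these health indicators, and assesses the wristband as a monitoring tool; because there is no concurrent comparison group, changes will not be attributed to an intervention.

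This wording covers Tasks 5 and 6 in Section 4, and Task 4 as association only.

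Two further edits are needed. Make the interventional label in Sections 7, 8 and 13 consistent with the new sentence. If the Section 3 interventions are delivered to these children, or evaluated elsewhere in the project, state where.

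The cost is a wording amendment, which goes through the approvals in Section 19 (the international supervisory committee and the regional ethics committee), and a more modest claim. Visits, measurements and sample do not change. Keeping the impact claim would instead need a defined intervention and a concurrent comparison group re-measured at 3 months, which is a change of design and not of wording.
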